### Background & Purpose of Research

## Describe the purpose, specific aims or objectives and specify the hypotheses or research questions to be studied:

For this study, we hypothesize that use of movable wheelchair arm rest device during inpatient therapy will lead to significantly greater improvements in UE motor recovery than conventional treatment. (For a demonstration video of the movable wheelchair arm rest device, please visit: <https://youtu.be/RfbaOGhJfug>). Our Aim is to perform a randomized controlled trial of the movable wheelchair arm rest device with inpatients with subacute stroke in three different inpatient rehabilitation facilities (N=58; Months 6-24). UCI will be one of the study sites. Rancho Los Amigos Rehabilitation center and Casa Colina Hospital and Centers for Healthcare will potentially be the other two study sites. We are in the process of negotiating the contracts between sites. Participants will be >3 days and <3 weeks post-stroke, with initial FM scores <4239. Participants will be randomized to receive the movable wheelchair arm rest device or an electronic exercise program and instructed to practice moving their arm between therapy sessions. The primary outcome measure will be change in FM score from baseline to three-months post-stroke. We hypothesize that participants who receive movable wheelchair arm rest device will have significantly greater improvements in FM score than control ( $p < 0.05$ , RM-ANCOVA) without an increase in pain or spasticity, if they exceed the putative threshold of UE motor drive needed for recovery. Success Criteria: A significantly greater increase in FM of >4.25 points (the FM MCID40) between movable wheelchair arm rest device and control at three months.

At project end, we will have validated the clinical feasibility and efficacy of the movable wheelchair arm rest device and optimized it for production and mass distribution. If our plan is successful, we will have demonstrated that wheelchair-based "rocking therapy" can help patients routinely achieve the threshold level of sensory motor drive needed to provoke true UE recovery.

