## Sample Size Determination:

1. Explain how the overall target sample size was determined (e.g., power analysis; precision estimation). Power analysis should (at least) match the primary outcome/endpoint.
2. Provide justification of the effect size for the primary outcome based on preliminary data, current knowledge/literature and/or cost consideration.
3. If appropriate, provide sample size justification for secondary outcomes.

Based on a power analysis using data from our previous LARA RCT with individuals with subacute stroke (n=19)36, enrolling 29 participants in each group, brings a total of 58 from 2 groups, will provide an 80% chance to demonstrate a significant difference in FM between the device and control at the three-month follow up ( $\alpha = 0.05$ ), assuming a dropout rate of 10%.

---

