## **Study Design & Statistics**

## **Include an explanation of the study design (e.g., randomized placebo-controlled, cross-over, cross-sectional, longitudinal, etc.) and, if appropriate, describe stratification/randomization/blinding scheme:**

This is a randomized controlled phase II clinical trial designed to test if use of movable wheelchair arm rest device reduces arm impairment compared to conventional training, in addition to standard rehabilitation therapy.

We will recruit individuals with an acute or subacute stroke from the Acute Rehabilitation Unit at UCI Medical Center to participate in this study. Participants will have arm impairment, which we will confirm with the Upper Extremity Fugl-Meyer Motor Assessment. After baseline evaluation, study participants will be equally randomized into two groups: device group versus control group. Randomization will proceed by block allocation based on time of enrollment.

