## **Describe the statistical methods for the stated specific aims and hypotheses. The analysis plans should match the stated study specific aims and hypotheses:**

All reported data from this study will be disaggregated by sex to test for any potential bias due to this biological variable. Data will be analyzed using modified intention-to-treat analysis. That is, all participants will be included in the analysis if the follow-up assessment is available, regardless of any deviations from the protocol. The effect of treatment on the primary outcome measure will be assessed using a repeated measures analysis of covariance (RM-ANCOVA) to account for any baseline differences between groups or variability in treatment intensity, with follow-up comparisons performed using Bonferroni-corrected t-tests or Wilcoxon rank sum tests if the data violates the assumption of normality. We hypothesize the participants in the movable wheelchair arm rest device group will have significantly greater and clinically meaningful (i.e. >4.25 FM points) reductions in motor impairment than participants in the control group due to the increased dose of UE motor system activation. Using data from the sensors on movable wheelchair arm rest device, we will test if this effect depends nonlinearly on the number of repetitions performed with the device, consistent with recent meta-analyses of forelimb recovery in a rodent model of stroke. That is, we hypothesize that the movable wheelchair arm rest device will provide a benefit only if the dose exceeds a threshold. A key goal is to also identify that threshold (by making a graph for humans like the one for rats), which will enable us to move forward with effective clinical prescription and goal setting with the movable wheelchair arm rest device. Visual analog pain, spasticity, and FAC scores will also be analyzed using RM-ANCOVA to test for significant changes related to use of the device. All analyses will be reviewed by a statistical consultant in the Institute for Clinical and Translational Science at UC Irvine.

**Provide precise definitions of the study endpoints and criteria for evaluation; if the primary outcomes are derived from several measurements (i.e., composite variables) or if endpoints are based composite variables, then describe precisely how the composite variables are derived:**

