**Describe the statistical method(s) that will be used to analyze the primary outcome(s) or endpoints:**

t-tests with Bonferroni corrections, or Wilcoxon rank sum tests if the distributions fail the Lilliefors test for normality.

**If appropriate describe secondary or post hoc analyses of primary outcome(s) or other exploratory analysis and if necessary, provide a breakdown of the methods used per outcome or endpoint:**

The effect of treatment on each outcome measure will be assessed using a repeated-measures ANOVA

---

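### The plan hypothesises benefit without more pain or spasticity, but gives these outcomes only tests for a difference, so it has no criterion that could support 'no increase'

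*Combined protocol and SAP*

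**What the plan says.** The purpose and hypotheses field states that device users will improve more on FM than controls, "without an increase in pain or spasticity, if they exceed the putative threshold of UE motor drive needed for recovery". The success criterion that follows concerns FM alone: "A significantly greater increase in FM of >4.25 points".

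Pain (visual analogue scale) and spasticity (Modified Ashworth) are listed as secondary outcomes. The statistical methods field, whose own prompt asks that analyses match the hypotheses, gives them one sentence: "Visual analog pain, spasticity, and FAC scores will also be analyzed using RM-ANCOVA to test for significant changes related to use of the device". The field on secondary and exploratory analyses adds: "The effect of treatment on each outcome measure will be assessed using a repeated-measures ANOVA".

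The sample size field covers FM only: "enrolling 29 participants in each group" "will provide an 80% chance to demonstrate a significant difference in FM between the device and control at the three-month follow up", at alpha 0.05 and allowing for 10% dropout. The documents give no largest acceptable increase in pain or spasticity, no non-inferiority or equivalence test, no interval rule, and no SD for either score.

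**The concern.** A difference test can show that pain or spasticity rose. Failing to show a rise is not evidence that there was none, least of all in a small trial, where the data may be compatible with anything from a fall to a sizeable rise. The hypothesis makes a claim of absence, and the stated analyses answer a different question.

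What is at stake is the tolerability half of the conclusion. The risk section lists arm pain, muscle soreness and joint soreness as foreseeable effects of repetitive exercise, and the device arm is encouraged towards a target of 1000 repetitions a day. A reader of the final report will want to know how large an increase the data exclude. The plan does not commit to saying.

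**Working it through.** **The plan's own figure.** The dropout step is consistent: 29 × 0.9 = 26.1, so about 26 evaluable per arm. The 80% power for FM cannot be reproduced, because neither the SD nor the assumed difference is stated. There is no corresponding figure for pain or spasticity to check.

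**Inputs**
- Allocation is 1:1 ("study participants will be equally randomized into two groups: device group versus control group").
- Planned analysed number: 26 per arm, as above.
- Enrolled number: 37, from the renewal form (22 men and 15 women). The site counts agree: 2 + 12 + 23 = 37.
- Assumption: all 37 are analysed, split 19 v 18. The documents give neither the actual split nor the analysed number.
- Assumption: two-sided 5% test. The methods field states no alpha for these outcomes.
- Assumption: results are in SD units, because no SD is given.
- Assumption: baseline–outcome correlation r of 0 (unadjusted), 0.5 or 0.7. The documents give none.

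**Formulas**
- Standard error in SD units: SE = √(1 − r²) × √(1/n₁ + 1/n₂).
- 95% CI half-width = t(0.975, df) × SE, with df = n₁ + n₂ − 2, less one when adjusting for baseline.
- Probability that a true increase d is non-significant: from the noncentral t distribution with noncentrality d/SE.

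**Worked case, 19 v 18**
- √(1/19 + 1/18) = 0.329.
- Unadjusted: half-width 2.030 × 0.329 = 0.67 SD. For d = 0.5, the noncentrality is 0.5/0.329 = 1.52, which gives 68% non-significant.
- r = 0.5: SE = 0.866 × 0.329 = 0.285; half-width 2.032 × 0.285 = 0.58 SD; 60% non-significant.
- r = 0.7: SE = 0.714 × 0.329 = 0.235; half-width 2.032 × 0.235 = 0.48 SD; 46% non-significant.

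**Results**

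| Analysed | r | 95% CI half-width (SD) | True 0.5 SD increase non-significant | True 0.8 SD increase non-significant |
|---|---|---|---|---|
| 19 v 18 | 0 | 0.67 | 68% | 34% |
| 19 v 18 | 0.5 | 0.58 | 60% | 22% |
| 19 v 18 | 0.7 | 0.48 | 46% | 9% |
| 26 v 26 | 0 | 0.56 | 58% | 19% |
| 26 v 26 | 0.5 | 0.48 | 47% | 10% |
| 26 v 26 | 0.7 | 0.40 | 30% | 2% |

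If the planned 10% loss were applied to the 37 (17 v 16 analysed), the unadjusted half-width would be 0.71 SD and the 0.5 SD figure 71%. The renewal form reports no withdrawals and says follow-up is complete, so 19 v 18 is the better base case, although the no-withdrawal answer may cover one site only.

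The Ashworth scale is ordinal, so figures in SD units are only approximate for spasticity.

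**The case against.** Several points on the other side stand.

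- A reader might infer that the investigators will treat p>0.05 as proof of no harm. The documents do not say so. The methods sentence can be read as an ordinary search for harm. What the documents do support is narrower: they supply no criterion for the 'without an increase' clause.
- A reader might infer that the trial's main claim or its whole safety case fails. It does not. The success criterion is FM only, the p<0.05 in the hypothesis field belongs to the FM comparison, and the clause on pain and spasticity appears once, conditional on a dose threshold. Safety is also watched in other ways: monthly data review, unscheduled review after unanticipated problems, pain-based eligibility, and an instruction to stop and consult if pain arises. These are safeguards for participants; they do not estimate a between-arm difference.
- A reader might infer that a clinically relevant rise would probably go undetected. That cannot be shown. The documents define no clinically relevant increase and give no SD, and a 0.8 SD increase would be missed in only 9% to 34% of trials at 19 v 18.
- The planned model is covariate-adjusted, so unadjusted figures alone would exaggerate the imprecision. The range above allows for this. Adjustment narrows the interval without turning a difference test into evidence of absence.
- Adjusted differences with intervals come out of the planned model anyway, nothing forbids reporting them, and a statistical consultant is to review all analyses. True, but the plan does not commit to the intervals or tie the conclusion to them.

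**Conclusion.** The point holds as a mismatch between hypothesis and analysis for two secondary outcomes. The stated difference tests cannot support a conclusion of no increase in pain or spasticity, and no other criterion is given. The FM comparison and its success criterion are untouched.

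The size depends on assumptions about the analysed number and the baseline correlation. Across the cases shown for 19 v 18 and 26 v 26, the interval extends 0.40 to 0.67 SD either side of the estimate, and a true 0.5 SD increase would be non-significant in 30% to 68% of trials. Enrolment and follow-up are finished, so recruiting more participants is no longer a way to gain precision. What can still be settled is how the result is expressed.

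**What to change.** In the statistical methods field, and in the report now being prepared:

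1. Report the baseline-adjusted between-arm difference in pain and in spasticity at discharge and at three months, each with a two-sided 95% CI.
2. Base any statement of 'no increase' on the upper confidence limit, not on p>0.05.
3. Where the interval is wide, use wording such as: *no increase detected; an increase of up to X is not excluded*, with X the upper limit.

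No agreed margin is needed for this. The repeated-measures ANCOVA and the repeated-measures ANOVA now both named for these outcomes should be reconciled at the same time.

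The cost is plan and report wording only, with no new data, visits or participants. The one downside is that the 'without an increase' conclusion may have to be softened at this sample size.

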**Multi-Center Studies: If known, indicate the total number of subjects enrolled at ALL sites to date:**

For Rancho Los Amigo Rehab Center: 10 Males and 2 Females - total of 12 participants. For Casa Colinas Rehab Center: 10- males, 13 females - total of 23 participants

---

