## Does this protocol require a Safety Monitoring Plan?

Yes

- Feel free to cut and paste into this section from the following sources, as applicable:
  - For NIH-sponsored clinical trials, the Data Safety Monitoring Plan (DSMP) should be part of the grant application.
  - For industry sponsor-initiated clinical trials, a FDA-approved DSMP should be part of the Master Protocol or the Data Safety Monitoring Committee/Board Charter.
  - For protocols conducted at the Institute for Clinical and Translational Science (ICTS) or Cancer Center (PRMC), the DSMP information approved by one of these committees should be inserted into this section
- **REQUIRED!** Submit the following documents, as applicable in the Attachments section:
  - Signed DSMB recommendation forms from independent DSMB.
  - The finalized DSMB charter must be submitted before enrollment begins.

**Provide details of those individuals who will be responsible for the safety oversight of your protocol, including the relevant experience/expertise of each individual (for UCI investigator initiated studies conducted only at UCI, provide the names and titles as well):**

The Data Safety Monitoring Board for the current study will be the research team that comprises individuals with various academic backgrounds:

- [name]., has experience in human subjects' research in stroke rehabilitation
- [name], has experience in human subjects' research in the areas of biomechanics, neural control of movement, and rehabilitation.
- [name] PT,DPT, is a licensed Physical Therapist with over 20 years' experience in stroke rehabilitation treatment and research.
- [name], PT, DPT, PhD, is a professor at the Department of Physical Therapy at Chapman University. She has over 25 years' experience in stroke rehabilitation treatment and research.

**Indicate how frequently accumulated protocol data will be reviewed and evaluated for participant safety, protocol conduct and progress, and, when appropriate, efficacy:**

The DSMB reviews study data monthly to evaluate the course of data collection with healthy and stroke subjects and to evaluate safety concerns. Efficacy is evaluated when enrollment ceases for each phase.

**Describe the events that would trigger an unscheduled review. Also include stopping guidelines and un-blinding rules if applicable:**

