## Provide a detailed chronological description of the procedures:

Participants will be invited for an initial assessment within three days of admission to an IRF to confirm they meet the inclusion criteria and to establish a baseline measure. Those who qualify will be randomly assigned to either the movable wheelchair arm rest device group or the control group. To ensure matched levels of impairment between groups, subjects will be stratified by their FM score into two levels (0-21, 22-42) and then randomized by alternating block allocation based on the time of enrollment. Individuals in the device group will be provided with a wheelchair equipped with movable wheelchair arm rest device and trained how to use it to perform stationary reaching practice and to help them ambulate. Once participants are competent, they will be instructed to perform stationary reaching practice and to use the movable wheelchair arm rest device to ambulate around the inpatient facility, with a target dose of 1000 device "reps" per day, which we estimate will take about 30 minutes of device use at around 1 rep every 2 seconds. The supervising therapist will customize the range of motion needed for device's integrated electronics to count a "rep" based on each patient's abilities. Participants in the control group will be given an electronic home exercise program (HEP) of proximal arm exercises developed by study therapists. They will be encouraged to exercise for 30 minutes a day with the electronic HEP (i.e. to match the duration with device). A supervising therapist will check in with all participants once per week to check on engagement with their exercise program and to troubleshoot any issues with device or the electronic exercise program. To measure compliance and quantify dose, the device will report the date, time, and number of repetitions completed for each movement type (stationary/overground) throughout the study using integrated electronics. Using technology, we previously developed for another study, the electronic exercise program provided to control participants will record how long the book is opened each day with a hidden magnetic sensor and data logger. Participants in both groups will continue therapy for the duration of their inpatient stays (average length of stay for individuals with moderate to severe impairment is 14 to 22 days, respectively, based on 104, n = 4142). The actual length of stay for each participant will be quantified and included as a covariate in the data analysis. Once participants are discharged, they will receive a post-therapy assessment and they may be allowed to keep the device and the exercise program based on the therapists' recommendations for the duration of the study. Participants will return three months following stroke onset for a final assessment. We would like to utilize the Tenovi Gateway device to collect the amount of use data. This data will be automatically uploaded to secure web portal through a Tenovi Gateway device, which plugs into the wall at subjects' rooms at the Acute Rehab Unit and or subjects' homes, automatically communicates with the exercise repetition counts through bluetooth, then uploads the data to the web portal through a low-speed cellular data connection. A study team member may visit participants' homes to set up the devices.

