#### **A bullet point list is recommended.**

The possible risks and/or discomforts associated with the procedures described in this study include the Following:

- Repetitive movement exercise may cause muscular fatigue (make the subject's muscles feel tired), muscle soreness, joint soreness, or arm pain. The subject will be instructed to cease exercise and consult the supervising therapist and physician if any pain arises from the exercise.
- There is a small risk of having the subject's fingers or hand or arm pinched or bruised by the device. The subject will be trained on how to use the device appropriately to avoid this risk.
- There is a risk of a breach of privacy if someone unrelated to the study obtains the videotapes of the subject, but the study investigators will protect against this risk by storing the tapes in a locked cabinet with a coded identifier. The subject will be asked for consent if the investigators wish to use any of the videotapes for publication or presentation of the study.
- Unknown risks: There may be risks related to the research that we don't know about yet. However, the subject will be informed of any additional risks to which he or she may be exposed, and any changes that are made to the study, as a result of any newly-identified risks.

**EXPEDITED/FULL COMMITTEE ONLY:** Include an assessment of their expected frequency (e.g., common – 65%, less common – 40%, unlikely – 5%, rare - <1%) and the seriousness (mild, moderate, severe).

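### The plan hypothesises no rise in pain or spasticity but names only difference tests for it, and at about 18 to 26 per arm a non-significant result cannot support that statement

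*Combined protocol and SAP*

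**What the plan says.** In the combined protocol and SAP, Background & Purpose of Research states the hypothesis of greater Fugl-Meyer (FM) improvement and attaches a safety clause: "without an increase in pain or spasticity, if they exceed the putative threshold of UE motor drive needed for recovery".

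Under Study Design & Statistics, the paragraph on statistical methods gives the analysis for these outcomes: "Visual analog pain, spasticity, and FAC scores will also be analyzed using RM-ANCOVA to test for significant changes related to use of the device". The answer on secondary and post hoc analyses adds: "The effect of treatment on each outcome measure will be assessed using a repeated-measures ANOVA". Both are tests for a difference in mean scores. Neither section gives a tolerable increase, a confidence interval or a definition of harm for pain or the Modified Ashworth scale.

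The sample-size section powers FM only, with 29 per arm, "assuming a dropout rate of 10" per cent. The renewal form reports enrolment complete with 37 adults, including "For Rancho Los Amigo Rehab Center: 10 Males and 2 Females - total of 12 participants", and says that all follow-up assessments are finished and analysis is under way.

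Participants are protected individually. Under Risk Assessment: "The subject will be instructed to cease exercise and consult the supervising therapist and physician if any pain arises from the exercise". Under Project Procedures: "A supervising therapist will check in with all participants once per week to check on engagement with their exercise program". Under Safety Monitoring Plan: "The DSMB reviews study data monthly to evaluate the course of data collection with healthy and stroke subjects and to evaluate safety concerns". Adverse events are also collected locally. None of these is described as a comparison between arms.

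**The concern.** A hypothesis of no increase needs an analysis that can limit how large an increase is still plausible. A test for a difference does not do that: a p-value above 0.05 can mean no effect, or a real effect in too small a sample. With power set for FM alone and enrolment below plan, the second explanation is hard to dismiss.

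At stake is the safety statement for a device not approved for marketing, whose listed risks include joint soreness and arm pain. If the report follows the plan literally, the reader sees a p-value and not the range of differences the data allow.

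**Working it through.** **Sample size inputs**

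- Planned: 29 per arm less 10% is 29 × 0.9 = 26.1, about 26 evaluable. In reverse, 26 / 0.9 = 28.9, which rounds up to 29, so the plan's dropout step is consistent.
- The 80% power for FM cannot be reproduced, because no FM difference or standard deviation (SD) is given for that calculation. Solving backwards, 26 per arm gives 80% power for about 0.79 SD (t-test, two-sided 0.05).
- Enrolled: 2 + 12 + 23 = 37, which agrees with 22 men + 15 women. Allocation is equal by design, so 37 / 2 = 18.5, about 18 per arm. Counts by arm are not given, so the even split is an assumption.

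**Power for a worsening of 0.5 SD** (two-sided 0.05; sidedness is not stated and is assumed)

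The noncentrality is 0.5 × √(n/2).

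| | n = 18 | n = 26 |
|---|---|---|
| Noncentrality | 1.50 | 1.80 |
| Power, normal approximation | Φ(1.50 − 1.96) = 32% | Φ(1.80 − 1.96) = 44% |
| Power, t-test | 31% | 42% |
| Power, ANCOVA, assumed baseline correlation 0.5 | 39% | 53% |
| Difference detectable with 80% power (t-test) | 0.96 SD | 0.79 SD |

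The ANCOVA row divides the effect by √(1 − 0.5²) = 0.866. Even with that gain, a true half-SD worsening is missed in about 47% to 61% of trials.

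**What a non-significant result leaves open**

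The 95% half-width, in SD units and without baseline adjustment, is t(0.975, 2n − 2) × √(2/n).

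- n = 18: 2.032 × 0.333 = 0.68 SD
- n = 26: 2.009 × 0.277 = 0.56 SD

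If the observed difference were exactly zero, the upper limit would still exceed half an SD at both sizes. The documents give no SD for pain. Assuming 2 to 3 points on the 10-point scale, the half-width is 1.4 to 2.0 points at 18 per arm and 1.1 to 1.7 at 26. Excluding a 0.5 SD increase with 80% power at one-sided 0.025 would need 2 × (1.960 + 0.842)² / 0.5² = 62.8, that is 63 per arm.

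**What the interval adds: an illustration on assumed distributions**

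Suppose 20% of device users and 4% of controls worsen by 4 pain points at one site, the others do not change, and rating noise has SD 0.75. In simulation the ANCOVA was non-significant in 77% of trials at 18 per arm and 67% at 26. Among those non-significant trials the median upper 95% limit was 1.4 and 1.2 points. With no true difference it was 0.6 and 0.5. The interval thus carries information that the p-value discards.

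**The case against.** The strongest reply is that no error is planned. The RM-ANCOVA is worded as a test to detect changes. The clause is a hypothesis conditional on exceeding a dose threshold, the success criterion concerns FM only, pain and spasticity are secondary, and a statistical consultant will review all analyses. This stands in part. A reader might infer that the trial will report absence of harm because p exceeds 0.05; no section says so. What remains is that the plan states the hypothesis and names nothing that could support it.

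A reader might also infer that harm goes unmonitored. The documents do not support that: the safeguards quoted above exist, and the renewal form reports no withdrawals, no promptly reportable problems and no change in risk and benefit. Those answers are not broken down by arm, so they do not fill the analytic gap. The attached activity schedule and post-therapy survey were not available and could hold more detail.

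A third tempting reading is that means hide a few marked worseners and counts by arm are more reliable. The documents give no distribution to establish this, and it depends on low rating noise. In the same kind of model, with noise SD 1.75, improvement among the unharmed in the device arm only, and worsening counted at either of two sites, a rise of 2 or more pain points occurred in 24.3% of device users and 26.5% of controls. That is the wrong direction despite true harm of 20% against 4%. At one site with SD 2.0 the contrast shrank to 22% against 19%. Counts are also imprecise: 4/18 against 1/18 is a difference of 16.7 percentage points (95% CI −7.5 to 40.1).

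Two further objections stand as limits on the fix. An interval without a margin does not demonstrate safety. Two pain sites and two Ashworth joints at two visits make eight intervals; if independent, the chance that at least one falsely excludes zero is 1 − 0.95⁸ = 34%.

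**Conclusion.** The concern holds as a mismatch between hypothesis and analysis. Planned power for a half-SD worsening is about 31% to 42%, or 39% to 53% with baseline adjustment at a correlation of 0.5. A non-significant RM-ANCOVA could not support a statement of no increase.

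This rests on an even split of the 37 enrolled for the lower size, and on the planned 10% loss for the upper. Half an SD is a reference effect chosen here, not a figure from the documents, and every result in pain points uses an assumed SD. The mean test would pick up large average shifts: for 2 points at SD 2, power is 85% at 18 per arm and 95% at 26.

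The change is worth making because it alters what the trial may say about safety. It does not show that harm occurred or that the RM-ANCOVA should be replaced.

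**What to change.** Keep the RM-ANCOVA and add the following.

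1. For pain and for Ashworth, report the adjusted device-minus-control mean difference with its 95% confidence interval at discharge and at three months. Do this separately for each site recorded in both arms at baseline and follow-up. The two lists of measures differ; the sites common to both are shoulder and hand for pain, elbow and wrist for Ashworth.
2. Label the intervals as descriptive and unadjusted for multiplicity.
3. Do not conclude that there was no increase from p > 0.05. State the largest increase the interval leaves possible. No margin was set before data collection, so the interval should not be presented as a non-inferiority result.
4. Optionally, show counts by arm of marked worsening from the participant's own baseline, for example pain up 2 or more points and Ashworth up 2 or more grades. Give these per site and never as worsening at any site, labelled post hoc, with no significance test, and not presented as more reliable than the mean difference.

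The cost is a few lines of text and the reporting of scores already collected, with no new visits, staff or participants. The downside is wide intervals and a more cautious safety statement.
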